4.3.6 Population of Imputation Models

All analyses on the AChR+ population will use an imputation model fitted on AChR+ only. Analyses on OP, MuSK, or LRP4 will use the OP to fit the imputation model.

4.3.7 Hierarchy of Secondary Endpoints

The primary and secondary endpoints will be tested using a hierarchical gatekeeping procedure. Where the hierarchical gatekeeping procedure is used, if any test result is not statistically significant, formal testing of subsequent endpoints will not occur. If the primary endpoint is statistically significant, the confirmatory secondary endpoints are tested in the following order:

- 1. Mean change from baseline in QMG score in AChR+ participants at Week 24
- Mean change from baseline in MG-QOL 15r total score in AChR+ at Week 24
- 3. Mean change from baseline in MGC total score in AChR+ participants at Week 24
- 4. Mean change from baseline in MG-ADL score in the OP at Week 24
- 5. Mean change from baseline in QMG score in the OP at Week 24
- 6. Proportion of AChR+ participants receiving rescue therapy between baseline and Week 24
- 7. Mean change from baseline in MG-ADL score in MuSK+ and LRP4+ at Week 24
- 8. Mean change from baseline in Neuro-QoL Fatigue Subscale total score in AChR+ participants at Week 24.

4.3.8 Software for Computation of Primary and Secondary Endpoints Analysis

The implementation of the previous described analyses will be conducted using the programing language R. The estimand framework will be implemented using the rbmi package. The statistical analysis will be conducted using the programing languages SAS and R.

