- The hierarchical gatekeeping has been updated to include mean change from baseline in Myasthenia Gravis Activities of Daily Living (MG-ADL) score in MuSK + and LRP4 + patients at Week 24 to align with the Statistical Analysis Plan (Section 6.4.3).
- The name of a Roche policy on data sharing has been corrected (Section 9.5).

Additional minor changes have been made to improve clarity and consistency. Substantive new information appears in italics. This amendment represents cumulative changes to the original protocol.

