# 6.4.3 Type I Error Control

The primary and secondary endpoints will be tested using a hierarchical gatekeeping procedure. Where the hierarchical gatekeeping procedure is used, if any test result is not statistically significant, formal testing of subsequent endpoints will not occur. If the primary endpoint is statistically significant, the confirmatory secondary endpoints are tested in the following order:

- 1. Mean change from baseline in QMG score in AChR+ patients at Week 24
- 2. Mean change from baseline in MG-QOL 15r total score in AChR+ patients at Week 24
- 3. Mean change from baseline in MGC total score in AChR+ patients at Week 24
- Mean change from baseline in MG-ADL score in the overall population (OP) at Week 24
- 5. Mean change from baseline in QMG score in the OP at Week 24
- Proportion of AChR + patients receiving rescue therapy between baseline and Week 24
- 7. Mean change from baseline in MG-ADL score in MuSK and LRP4 patients at Week 24
- 8. Mean change from baseline in Neuro–QoL Fatigue Subscale total score in AChR+patients at Week 24

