2.2 SAMPLE SIZE DETERMINATION

Determination of sample size is based on all globally enrolled participants. In this study, approximately 185 participants will be enrolled and randomized in a 1:1 ratio to each treatment group (satralizumab or placebo). Randomization will be stratified by baseline SOC treatment, region, and auto-antibody type as described in the Study Protocol, Section 3.1.

The estimated sample size required to demonstrate efficacy with regard to the MG-ADL is based on the AChR+ population and the following assumptions:

- The primary hypotheses test in the AChR+population is the difference between the placebo and satralizumab groups in the change from baseline to Week 24 in total MG-ADL score
- The assumed change from baseline to Week 24 in the placebo group is 2.3 points
- The assumed change from baseline to Week 24 in the satralizumab group is 4.3 points
- The assumed change from baseline accounts for approximately 10% of participants in the satralizumab group and approximately 20% of participants in the placebo group receiving rescue therapy
- The standard deviation (SD) of the change from baseline to Week 24 is 3.97 in both the placebo and satralizumab groups
- The assumed study treatment withdrawal rate is 10%

The assumptions are based on data reported in Howard et al. (2017). Due to changes in the treatment landscape the assumed mean change from baseline to Week 24 in the satralizumab arm is now assumed to be 4.3 (instead of 4).

Based on these assumptions and using a two-sided α level of 0.05, the sample size to achieve 85% power was estimated at 160 participants (80 per group) in the AChR+ population. Under the assumption that up to 25 participants meeting the study eligibility criteria will be AChR- (MuSK+ or LRP4+), the total study sample size will be approximately 185 participants. This sample size also provides approximately 80% power for an analysis of the difference between the placebo and satralizumab groups in the proportion of MG-ADL responders in the mITT and AChR+ population. This power calculation assumes a 50% response rate in the placebo group and a 75% response rate in the satralizumab group.

3. ANALYSIS SETS

The following populations are defined (Table 3):

Table 3 Analysis Sets

Population	Definition
Intent to treat (ITT)	All randomized participants. This excludes adolescents joining the study after the last adult participant is randomized.

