4.3.5 Secondary Endpoint of Rescue Therapy

The endpoint of proportions of participants receiving rescue therapy during the double—blind period will analyze the variable that encodes whether a participant received rescue therapy during the double-blind period or not. Treatment policy is used, that is if a participant stops study drug but receives rescue therapy during the safety follow-up and this occurs within 24 weeks of baseline then this is counted as having received rescue therapy. Stop of study drug and no further information available will be imputed as not having received rescue therapy.

A Cochran-Mantel-Haenszel test over the treatment groups stratifying for baseline stratification factors is the treatment effect estimator for the proportions of participants receiving rescue therapy. The estimate is the difference in proportion at Week 24.

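### Does putting the small MuSK+/LRP4+ test ahead of Neuro-QoL Fatigue make the testing hierarchy faulty?

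*SAP*

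**What the plan says.** SAP 4.3.7 tests the primary endpoint and then eight confirmatory secondary endpoints in a fixed order, with the rule that "if any test result is not statistically significant, formal testing of subsequent endpoints will not occur". Step 6 is the proportion of AChR+ participants given rescue therapy. Step 7 is "Mean change from baseline in MG-ADL score in MuSK+ and LRP4+ at Week 24". Step 8 is "Mean change from baseline in Neuro-QoL Fatigue Subscale total score in AChR+ participants at Week 24".

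Protocol 6.4.3 has the same order, with step 7 worded as "Mean change from baseline in MG-ADL score in MuSK and LRP4 patients at Week 24". The Version 5 amendment rationale records the addition: "The hierarchical gatekeeping has been updated to include mean change from baseline" in MG-ADL for this group, to bring the protocol into line with the SAP.

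SAP 2.2 sizes the trial on the AChR+ population: 80 per group for 85% power, with a 2-point difference (4.3 against 2.3), SD 3.97 and 10% withdrawal. The AChR-negative group is capped at 25. The same section assumes "approximately 10% of participants in the satralizumab group and approximately 20% of participants in the placebo group receiving rescue therapy". Neither document states an effect or a power for step 7 or step 8.

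**The concern.** Under a stop-at-first-failure rule, an endpoint is formally tested only if everything ahead of it succeeds. The usual advice is to put well-powered tests early. Here a test in at most 25 patients gates one in a population about six times as large (160/25 = 6.4), and it follows a rescue-therapy test that is itself weak. Fatigue is labelled confirmatory in SAP Table 6, yet it looks unlikely ever to be formally tested. At stake is the formal fatigue claim only: fatigue would still be estimated and reported. Exchanging two lines before unblinding seems to cost nothing in alpha.

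**Working it through.** **The plan's own figure.** Inputs from SAP 2.2: difference 2, SD 3.97, two-sided α 0.05, power 85%, withdrawal 10%.

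n per arm = 2 × (1.960 + 1.036)² × 3.97² / 2² = 70.8, so 71. Then 71/0.9 = 78.9, so 79 per arm and 158 in total. The t-test version needs 72 per arm, and 72/0.9 = 80, which is the stated 160. The figure reproduces.

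**Step 7.** Assume the AChR+ difference and SD carry over, with 12 and 13 patients per arm.

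- Standard error = 3.97 × √(1/12 + 1/13) = 1.589.
- Noncentrality = 2/1.589 = 1.258, with 23 degrees of freedom and critical t = 2.069. Power = 22.6%.
- Smallest significant observed difference = 2.069 × 1.589 = 3.29 points.
- Other assumptions: SD 3.2 gives 32%, a 3-point effect 44%, a 4-point effect 67%.

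**Step 6.** Rescue 10% against 20%, 80 per arm, pooled variance under the null.

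- Null standard error = √(2 × 0.15 × 0.85/80) = 0.0565.
- Alternative standard error = √((0.10 × 0.90 + 0.20 × 0.80)/80) = 0.0559.
- z = (0.10 − 1.960 × 0.0565)/0.0559 = −0.19, so power = 42.4%.

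**Reaching step 8, given that steps 1 to 5 succeed.** 0.424 × 0.226 = 9.6%. Multiplying is an approximation. If step 6 is allowed to correlate 0.3 to 0.7 with the primary (an assumption), its conditional power is 44.7% to 47.2%, and the result is 10% to 11%.

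**What a swap would do.** The documents give no fatigue effect, so the standardised effects below are assumptions. The last, 0.504, is the primary's own (2/3.97). All figures are conditional on steps 1 to 5 succeeding.

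| Assumed fatigue effect (SD) | Fatigue power, 80 per arm | Fatigue claim: now → swapped | MuSK+/LRP4+ claim: now → swapped |
|---|---|---|---|
| 0.30 | 47.1% | 4.5% → 20.0% | 9.6% → 4.5% |
| 0.45 | 80.8% | 7.8% → 34.3% | 9.6% → 7.8% |
| 0.504 | 88.6% | 8.5% → 37.6% | 9.6% → 8.5% |

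Whichever endpoint stands last succeeds with the product of all three powers. The first row, for example, is 0.424 × 0.226 × 0.471 = 4.5%.

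**Type I error.** A false claim in a fixed sequence requires rejecting the first true null hypothesis in the list, and that test is run at 0.05. The familywise error is therefore at most 0.05 in any order, whatever the power of each step. The present order and the swapped order are equally valid on this count.

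**Was the small group overlooked?** No. Protocol Version 5 added the test. SAP Version 3 then returned to this population: its amendment rationale cites the few LRP4+ participants and the distinct nature of MuSK+ disease, and adds a MuSK+-only analysis, which Table 6 labels exploratory. The pooled test stayed confirmatory and stayed seventh.

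**The case for a change.** The best argument for a swap is efficiency. Write p6, p7 and p8 for the three powers. The fatigue claim gains p6·p8·(1 − p7) and the MuSK+/LRP4+ claim loses p6·p7·(1 − p8). The gain exceeds the loss whenever p8 > p7, that is, whenever fatigue power exceeds 22.6%, a standardised effect of only about 0.19. Even with a true 4-point effect in MuSK+/LRP4+ patients, step 7 would block fatigue about one time in three. No scientific reason for the position of step 7 is written down, and SAP Version 3 already makes changes before unblinding because of small numbers, such as pooling Europe with North America.

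All of that arithmetic stands, and so does the remark about the missing reason. It falls short as a criticism on three counts.

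- Counting claims gives a fatigue claim and a claim in a separate serotype equal value. That weighting belongs to the sponsor. At a fatigue effect of 0.30 SD, the swap roughly halves the chance of the MuSK+/LRP4+ claim (9.6% to 4.5%).
- Step 6 is a bottleneck in either order. On the planning rates, fatigue would still go unclaimed in 62% to 80% of cases after a swap. The SAP Version 3 rationale also notes that few rescue treatments were given, without a rate. As illustrations only, 5% against 10% gives step 6 about 22% power, and 2.5% against 5% about 13%. The fatigue claim after a swap would then be about 11–20% or 6–11%.
- The change is less trivial than one line. Protocol 9.7 requires approval for amendments that are more than logistical or administrative, although SAP Section 1 lets the SAP override the protocol's analyses for filings.

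One might also query the step 6 rule that "Stop of study drug and no further information available will be imputed as not having received rescue therapy". With four such participants (assumed), all on satralizumab, step 6 power moves from 42.4% to 46.5%; all on placebo, to 36.5%. This has no settled direction and no bearing on whether step 7 should precede step 8.

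**Conclusion.** The concern does not hold. The sequence is valid, both documents give the same order, and no stated figure or property of the plan is wrong. Step 7 is weak (about 23% power at 25 patients) and step 8 is unlikely to be formally tested (about 10%, given success at steps 1 to 5). Both figures rest on carrying the AChR+ effect and SD over to MuSK+/LRP4+ patients and on the planned rescue rates. They describe the price of a priority that was set deliberately and kept with the small numbers known. A swap would buy a better chance for fatigue, of a size that depends on an effect the documents do not give, and would pay for it with the MuSK+/LRP4+ claim. Reasonable statisticians could choose either order. The primary analysis, steps 1 to 5 and the estimation of fatigue are unaffected.

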4.4 EXPLORATORY ENDPOINTS ANALYSES

Exploratory endpoints analyses are listed in Table 6.

4.4.1 Sustained Efficacy

To demonstrate evidence of sustained efficacy of satralizumab, the mean change from baseline to OLE Week 48 will be fitted using an MMRM for both the MG-ADL and the QMG in OP, AChR+ and AChR- participants. This analysis will include participants who at the time of the clinical cutoff (CCOD) have been enrolled for at least 40 weeks, i.e. with at least an OLE Week 16 visit for those still part of the study.

4.4.2 Additional Evidence of Efficacy

4.4.2.1 Time to Disease Improvement and Disease Worsening

Time-to-event analyses of the following endpoints will be conducted on mITT participants during the double-blind period.

Time to disease improvement (composite endpoint):

- ≥2 point reduction in total MG-ADL score
- ≥3 point reduction in QMG score
- ≥3 point reduction in MGC score
- MG-ADL score of 0 or 1 (minimal symptom expression status)
- Combination (whichever happens first) of reduction by ≥2 points in total MG-ADL or ≥3 points in total QMG score

Time to disease worsening:

- Time to first use of rescue therapy
- Time to MG-related exacerbation.

Participants with no event during the double-blind period will be censored on the day of their last double-blind period visit. The time of each event will be derived from the actual time point the event first occurs compared to the timepoint of baseline. The first four endpoints will use a composite strategy for rescue therapy, i.e., participants will be coded as not having had an event if they receive rescue therapy during the double-blind period and they will be censored at the time they receive rescue therapy. The treatment effect will be estimated using a log-rank test. Kaplan-Meier curves will be used to plot the data and listings will contain survival estimates at regular time points.

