1.1 OBJECTIVES AND ENDPOINTS

This study will evaluate the efficacy, safety, PK, and pharmacodynamics (PD) of satralizumab compared with placebo in participants with gMG on stable background therapy. In addition, the study will assess the long-term safety and efficacy of satralizumab during the open-label extension (OLE) period.

The study has the following objectives and corresponding endpoints (Table 1).

Table 1 Objectives and Corresponding Endpoints

Primary Efficacy Objective	Corresponding Endpoint
To evaluate the efficacy of satralizumab versus placebo on function in daily life in the AChR+ population	Mean change from baseline in total MG-ADL score at Week 24
Secondary Efficacy Objectives	Corresponding Endpoints
To evaluate the efficacy of satralizumab versus placebo on function in daily life in the OP	Mean change from baseline in total MG-ADL score at Week 24
To evaluate the efficacy of satralizumab versus placebo in the AChR+ and OP on:	
 Function in daily life 	Percentage of participants with a ≥2-point reduction from baseline in total MG-ADL score at Week 24 ^a
 QMG, QoL, and Fatigue 	Mean change from baseline in QMG score, MG-QOL 15r total score and Neuro-QoL Fatigue Subscale total score at Week 24
	Percentage of participants with a ≥3-point reduction from baseline in QMG score at Week 24 ^a

 Table 1
 Objectives and Corresponding Endpoints

	- Clinical status	•	Mean change from baseline in total MGC score at Week 24
		•	Percentage of participants with a ≥3-point reduction from baseline in total MGC score at Week 24 ^a
	 Disease severity 	•	Proportion of participants:
		•	Who have achieved minimal symptom expression (total MG-ADL score of 0 or 1) at Week 24 a
		•	With at least one gMG-related exacerbation between baseline and Week 24
		•	Receiving rescue therapy between baseline and Week 24
•	To evaluate the durability of the efficacy of satralizumab versus placebo in the AChR+ population and the OP	•	Duration (average number of consecutive months) of meaningful improvement, defined as ≥2-point reduction from baseline in total MG-ADL score ^a
	Exploratory Efficacy Objectives		Corresponding Endpoints
•	To evaluate the efficacy of satralizumab versus placebo in the AChR+ and OP on		
	- Time-to-event	•	Time to disease improvement as measured by:
			 ≥2-point reduction in total MG-ADL score or
			 ≥3-point reduction in QMG score or
			 ≥3-point reduction in total MGC score or
			 MG-ADL score of 0 or 1 (minimal symptom expression)

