4.3.4 Secondary Endpoints Under the Duration Estimand

The duration estimand is only relevant for the analysis of the number of consecutive visits a participant shows an MG-ADL reduction of at least 2 points from baseline. Based on the completed data set, the first time a participant shows a 2-point or more reduction from baseline, the duration is measured until Week 24 or until the visit when MG-ADL=is no longer reduced by 2 points from baseline MG-ADL. The duration is the difference in weeks between the two visits defining the start and end (or Week 24) of reduction from baseline. If the participant shows a reduction for only one visit, the count is set to 1 week. If the participant required rescue therapy, the count is stopped prior to the visit at which the participant received rescue therapy (composite).

The count variable (the number in weeks by consecutive visits) will be modeled using an ANCOVA adjusting for the same covariates as the imputation model and baseline MG-ADL. The treatment effect estimator is the regression coefficient of the treatment group. The estimate is the difference in the mean duration of meaningful improvement at Week 24.

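### Exploratory time to improvement (SAP 4.4.2.1): the rescue rule is called composite but censors at rescue, leaves improvement before rescue unclear, and gives no rule for the combination endpoint

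*SAP*

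**What the plan says.** SAP 4.4.2.1 lists five time-to-improvement endpoints, to be shown as Kaplan-Meier curves and compared by a log-rank test.

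- Rescue: "The first four endpoints will use a composite strategy for rescue therapy". The text then explains that "participants will be coded as not having had an event if they receive rescue therapy during the double-blind period and they will be censored"; the censoring date is fixed by "they will be censored at the time they receive rescue therapy".
- Everyone else without an event: "Participants with no event during the double-blind period will be censored on the day of their last double-blind period visit".
- Timing: "The time of each event will be derived from the actual time point the event first occurs".
- The fifth bullet starts "Combination (whichever happens first) of reduction by" and joins the MG-ADL and QMG criteria. SAP Table 1, under "Time to disease improvement as measured by", lists only the other four, as does protocol Table 2.

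The SAP uses the same label elsewhere. In 4.3.1.1 and 4.3.3 (responder), a rescued participant is a non-responder whatever the score. In 4.3.4 (duration), the count of improved weeks stops before the rescue visit, so improvement up to then is kept.

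The protocol gives rescue for myasthenic crisis, marked worsening, or danger to health without it (3.1.5). It judges onset of response with responder definitions that require no rescue (3.4.7), and treats rescued patients as non-responders (3.4.7.4).

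**The concern.** There are three problems in one paragraph.

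1. **Label and operation disagree.** Censoring removes the participant from the risk set and lets those still followed stand in for them. That answers what would have happened without rescue. A composite counts rescue as failure to improve. The stand-in assumption is doubtful when rescue follows worsening.
2. **Improvement before rescue.** The text does not settle whether a participant who improved and was rescued later has an event. Two programmers could produce different analyses. If the answer is no, an early event depends on later information.
3. **The combination endpoint.** It has no rescue rule of its own. Under the general censoring rule, improvement after rescue would count for it but not for its components.

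At stake is whether the curves and tests estimate the strategy that the SAP names, and whether they agree with each other.

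**Working it through.** The plan gives no event count, power or effect size for these endpoints, so there is no figure to reproduce. The check is a comparison of rules, followed by an illustration of size.

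**Censoring against composite, by hand.** Of 20 participants, 4 are rescued unimproved at Week 8 and 10 improve at Week 12. With censoring at rescue, 16 remain at risk at Week 12 and the Kaplan-Meier proportion improved is 10/16 = 62.5%. Under a composite it is 10/20 = 50%.

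**The same with planning figures (SAP 2.2).** Let c be the proportion improved, taken from the assumed responder rates (50% placebo, 75% satralizumab). Let r be the proportion rescued before improving, at most the planned rescue rate (20%, 10%). With constant competing hazards:

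- total cumulative hazard H = -ln(1 - c - r)
- improvement share H_I = H × c/(c + r)
- Kaplan-Meier with censoring at rescue = 1 - exp(-H_I); composite = c

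Placebo, r = 0.20: H = -ln 0.30 = 1.204; H_I = 1.204 × 0.50/0.70 = 0.860; result 57.7% against 50%.

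Satralizumab, r = 0.10: H = -ln 0.15 = 1.897; H_I = 1.897 × 0.75/0.85 = 1.674; result 81.3% against 75%.

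If only a quarter of rescues precede improvement (r = 0.05 and 0.025), the results are 51.6% and 76.4%.

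**Improvement before rescue.** Take a participant improved on MG-ADL at Weeks 4 to 12 and rescued at Week 16. Read literally, 4.4.2.1 gives no event and censors at Week 16. Read as covering only rescue before improvement (the narrow reading), it gives an event at Week 4. The duration rule in 4.3.4 keeps 12 - 4 = 8 weeks of improvement.

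**Combination endpoint.** Take a participant rescued at Week 6 whose first MG-ADL improvement is at Week 12, with no QMG improvement before rescue. Both components are censored at Week 6. If the combination is built from raw scores under the general censoring rule, it has an event at Week 12.

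**Simulated size.** The reference composite counts improvement before rescue as an event and keeps anyone rescued before improving at risk to Week 24. Shifts are the SAP rule minus this reference, in Week 24 Kaplan-Meier points; z is scaled to 80 per arm.

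- Exponential model: 50%/75% improved by Week 24, seen at protocol visits; rescue uniform over 24 weeks, from independent of improvement to confined to unimproved patients.
- Score-based model: MG-ADL Week 24 mean changes -2.3/-4.3, SD 3.97, within-patient correlation 0.5 to 0.85; rescue independent or likelier in worse patients; 18 settings.

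| Rescue, placebo/satralizumab | Model and reading | Placebo shift | Satralizumab shift | z shift |
|---|---|---|---|---|
| 4%/2% (assumed) | Exponential, literal | +0.3 to +1.4 | +0.2 to +1.2 | -0.04 to -0.02 (both readings) |
| | Exponential, narrow | +1.0 to +1.4 | +0.7 to +1.2 | |
| | Score-based | -1.0 to +2.2 (range over arms) | | -0.06 to +0.10 |
| 20%/10% (planned) | Exponential, literal | +1.1 to +8.0 | +1.0 to +6.0 | -0.26 to -0.09 (both readings) |
| | Exponential, narrow | +5.2 to +8.0 | +3.5 to +6.0 | |
| | Score-based, literal | -5.3 to +9.4 | -2.5 to +4.3 | -0.27 to +0.46 (both readings) |
| | Score-based, narrow | +3.8 to +11.9 | +2.2 to +5.6 | |

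The reference z in the exponential model at planned rates is 3.41 to 3.54. The literal reading can lower a curve because it erases real earlier improvements while censoring raises the curve; the two effects partly cancel.

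The reference matters too. If the composite makes anyone rescued a non-event to Week 24, as the responder rule does, a separate simulation at planned rates gives 40%/67 to 68%, against 46%/73% for the literal SAP rule.

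**The case against.** - **It is only a label.** The explanatory clause states the operation, so a programmer has one instruction for a participant rescued before improving. The strategy for an exploratory curve is the sponsor's choice, and renaming it hypothetical would cure the mismatch. This stands as an alternative fix, but it does not make the present label right.
- **The literal reading may be intended.** A reader might infer that the SAP wrongly deletes real improvements. The documents do not support that as established. The literal text, protocol 3.4.7 and 3.4.7.4, and SAP 4.3.3 favour no event after any rescue, although the protocol definitions are written for Week 24. Timing at first occurrence and the duration rule favour an event. What can be shown is an ambiguity.
- **The combination may inherit its components' rule.** A reader might infer that it must contradict them. If it is derived as the earlier of the two component event times, the conflict disappears. The SAP does not say how it is derived, so the conflict is possible, not certain.
- **Little depends on it.** The version 3 amendment rationale records few rescue administrations, and these endpoints are outside the testing hierarchy in 4.3.7. Both facts stand and keep the point minor.

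**Conclusion.** The point holds as a minor one. The composite label is wrong for censoring at rescue, with high confidence; the status of improvement before rescue is unclear; and the combination endpoint has no stated rescue rule.

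The effect is probably small, because the SAP reports few rescues. The 4%/2% figure is an assumption, since the documents give no observed rate; rescue timing and its link to outcome are assumptions as well.

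Two stronger conclusions are tempting. One is that the rule always inflates both curves, shrinks the arm difference and is therefore conservative. That fits the exponential scenarios, but in the score-based model z moves either way and, on the literal reading, so do the curves. The other is that an efficacy claim is affected. The primary endpoint and the confirmatory secondary endpoints do not use this rule, so no confirmatory conclusion changes.

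**What to change.** Reword SAP 4.4.2.1 before unblinding so that:

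1. a participant rescued before improving has no event and stays in the risk set to the last double-blind visit, replacing censoring at rescue;
2. the text states whether an improvement before rescue is an event, preferably yes and at its own time, so that no event depends on what happens later;
3. the same rule applies to the MG-ADL/QMG combination, with its derivation stated.

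If censoring at rescue is really wanted, keep it and call it a hypothetical strategy; items 2 and 3 are still needed.

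The cost is two or three sentences and a small programming change. No new data are needed: protocol 3.1.4 lets rescued patients continue to the end of the double-blind period, and 4.3.3 asks sites to keep them in the study.
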